6. Females only; a urine pregnancy test will be performed at Screening, on Day 1 (Baseline), and all subsequent visits (does not include trial medication only visits).
7. Includes measurement of blood pressure, respiratory rate and pulse rate (all sitting after 5 minutes rest). The patient's body temperature will also be recorded.
8. Findings of alanine aminotransferase or aspartate aminotransferase >3 times the upper limit of normal or hemoglobin <8.0 g/dL at baseline are criteria for exclusion.
9. Two consecutive recordings need to be taken.
10. Adverse events will be collected from the time of informed consent. Adverse events continuing at the EoT Visit must be followed to resolution or follow up as agreed by the Investigator and medical monitor. For patients who complete the trial or who discontinue the trial early, AEs will be captured for 10 weeks after the EoT visit.
11. Questionnaires will be completed at the site by the patient before any investigations or discussions about their disease with the clinic staff.
12. Pharmacokinetic (PK) and anti-drug antibody (ADA) samples (including neutralizing ADA samples) should be taken at each visit designated with an "X", and can be taken at any time during the visit (PK and ADA/neutralizing ADA samples will be taken at the same time point). For all PK samples, the day and time of sampling must be accurately recorded. All dosing dates and times must be accurately entered in the patient diary. See also [Table 5.4: 1](#) for PK sampling time points.
13. At the Screening visit, the administration of BI 695501 will be performed by a suitably qualified, designated trial personnel at the site and patients will be trained on self-administration. This will be the last administration of trial medication in Trial 1297.2.
14. The first dose of trial medication in the extension trial will be administered at the Baseline visit, which is approximately 2 weeks after the Screening visit (the Week 48 visit of Trial 1297.2). The patients will self-inject BI 695501 with the support of the suitably qualified, designated trial personnel.
15. For all subsequent injections. Patients will self-inject the trial medication every 2 weeks until trial completion or early withdrawal.
16. 1 to 5 syringes will be dispensed to the patient at each visit.

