### **3.3.2 Inclusion criteria**

1. All patients must sign and date an Informed Consent Form consistent with ICH GCP guidelines and local legislation prior to participation in the trial (i.e., prior to any trial procedures, which include medication washout and restrictions) and be willing to follow the protocol.
2. Adult patients with moderately to severely active RA who have completed Trial 1297.2, and who wish to participate in this extension trial and in the Investigator's assessment can benefit from receiving BI 695501.
3. Patients willing and able to self-administer BI 695501 pre-filled syringe.
4. For participants of reproductive potential (males and females), a reliable means of contraception has to be used throughout trial participation. Acceptable methods of birth control include, for example, birth control pills, intrauterine devices, surgical sterilization, vasectomized partner and double barrier method (for example male condom in combination with female diaphragm/cervical cap plus spermicidal foam/gel/film/cream/suppository). All patients (males and females of child-bearing potential\*) must also agree to use an acceptable method of contraception for 6 months following completion or discontinuation from the trial medication.

\*Women of childbearing potential are defined as:

- Any female who has experienced menarche and does not meet the criteria for "women not of childbearing potential" as described below

Women not of childbearing potential are defined as:

- Women who are postmenopausal (12 months with no menses without an alternative medical cause) or who are permanently sterilized (e.g., tubal occlusion, hysterectomy, bilateral oophorectomy or bilateral salpingectomy)

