13. Current inflammatory joint disease other than RA (e.g., gout, reactive arthritis, psoriatic arthritis, seronegative spondyloarthropathy, Lyme disease) or other systemic autoimmune disorder (e.g., systemic lupus erythematosus, inflammatory bowel disease, pulmonary fibrosis, or Felty's syndrome, scleroderma, inflammatory myopathy, mixed connective tissue disease, or any overlap syndrome). Secondary Sjögren's syndrome or secondary limited cutaneous vasculitis with RA is permitted.
14. Any planned surgical procedure, including bone/joint surgery/synovectomy (including joint fusion or replacement) for the duration of the trial.
15. Known active infection of any kind (excluding fungal infections of nail beds), or any major episode of infection requiring hospitalization or treatment with intravenous (i.v.) anti-infectives within 4 weeks of the Screening Visit or completion of oral anti-infectives within 2 weeks of the Screening Visit.
16. Serious infection or opportunistic infection during the 1297.2 trial.
17. Any acquired neurological, vascular, systemic or demyelinating disorder that might affect any of the efficacy assessments, in particular, joint pain and swelling (e.g., Parkinson's disease, cerebral palsy, diabetic neuropathy) that occurred during the 1297.2 trial.
18. Currently active alcohol or drug abuse.

19. Treatment with i.v. Gamma Globulin or the ProSORBA® Column during the 1297.2 trial.
20. Planned treatment with i.v. intramuscular, intra-articular and parenteral corticosteroids.
21. Aspartate aminotransferase (AST) or alanine aminotransferase (ALT) >1.5 times upper limit of normal (ULN).
22. Hemoglobin <8.0 g/dL.
23. Platelets <100,000/ $\mu$ L.
24. Leukocyte count <4000/ $\mu$ L.
25. Creatinine clearance <60 mL/min.
26. Patients who are currently participating in another clinical trial other than Trial 1297.2.

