### **3.3.4 Removal of patients from therapy or assessments**

#### **3.3.4.1 Removal of individual patients**

Patients who do not meet all of the inclusion criteria or who meet one or more of the exclusion criteria will not be enrolled in this extension trial. The primary reason for the screen failure will be recorded on the electronic Case Report Form (eCRF).

Patients have the right to withdraw from this trial at any time for any reason.

Two situations can occur in this trial and need to be documented accordingly, as follows:

1. An individual patient is to be withdrawn from the trial if:
  - The patient decides to discontinue participation in the trial by withdrawal of consent. In this case, no more investigations will be performed. The patient does not have to justify the decision.
2. Based on assessment by the Investigator, and after consultation with the trial medical advisor, an individual patient may be discontinued from treatment with the investigational compound if:
  - The patient needs to take concomitant drugs that interfere with the investigational product or other trial medication
  - The patient can no longer be treated with trial medication for other medical reasons (such as surgery, adverse or drug-related events, other diseases, or pregnancy)
  - Repeated protocol violation after documented discussion with the medical monitor
  - Lack of efficacy
  - The patient has an AE that is categorized as a serious infection. A serious infection is defined as infections requiring i.v. antibiotics or those that meet the regulatory definition of a SAE (including, but not limited to, systemic fungal infections, human immunodeficiency virus [HIV], HBV, HCV, infected joint prosthesis)
  - Patient lost to follow-up despite reasonable efforts to make contact with the patient

If a patient permanently discontinues trial medication for any reason, every effort should be made for the patient to attend the EoT Visit as soon after trial treatment discontinuation as possible. Every effort should be made for all patients who discontinue the trial treatment early, to return for a safety follow-up visit 10 weeks after the last dose of trial medication. For details of assessments to be performed at the Week 48 visit and the Week 58 visit, see [Sections 6.2.2](#) and [6.2.3](#), respectively.

For all patients the reason for withdrawal (e.g., AEs) must be recorded in the eCRF. These data will be included in the trial database and reported.

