## 6.2 DETAILS OF TRIAL PROCEDURES AT SELECTED VISITS

### 6.2.1 Screening period

#### Screening Period (Day -14)

Once the patient has provided informed consent (before any 1297.2 or 1297.3 trial-specific procedures or assessments are performed) and meets all inclusion criteria and none of the exclusion criteria (see [Section 3.3](#)), the trial site will enter the screened patient into the system using the Interactive Response Technology (IRT).

The following will also be performed/collected:

- Demographic information (including gender, date of birth, ethnicity and race), and medical and surgical history (including RA history and history of opportunistic infection)
- Evaluation of patient's willingness and ability to self-administer trial medication
- Physical examination, including height (cm) and weight (kg) (see [Section 5.3.1](#))
- Infection screen (HBsAg, HCV and HIV test, per the Investigator's discretion)
- Urine pregnancy test for women of child-bearing potential
- Patient questionnaires: global VAS, HAQ-DI and SF-36 v2 (see [Section 5.2](#))
- Joint assessment (see Section 5.2)
- TB test (QuantiFERON®-TB Gold test)
- ESR and CRP
- Physician questionnaire: global VAS (see Section 5.2)
- Vital signs (blood pressure, pulse rate, respiratory rate, and body temperature; see [Section 5.3.2](#))
- Laboratory testing (serum chemistry, hematology and urinalysis; see [Section 5.3.3](#))
- 12-lead ECG (see [Section 5.3.4](#))
- Previous and concomitant therapy (see [Section 4.2](#))
- Assessment of AEs (see [Section 5.3.6](#))

Once patients have signed the ICF, completed screening, and eligibility is confirmed, the Investigator will contact IRT and patients will be assigned to treatment with BI 695501. As part of the Trial 1297.2 Week 48 assessments, trial medication is administered. This is the last trial medication administration of the 1297.2 trial. During this visit, the Investigator/designee will train the patient on how to self-administer the trial medication. See [Section 4.1.4](#) for details.

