### 5.4. PER PROTOCOL ANALYSIS SET [PPAS]

No per protocol analysis set (PPAS) is defined in this trial.

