## 9.1. IMPORTANT PROTOCOL DEVIATIONS

Important protocol violations defined below will be listed for the ASD set:

- Trial drug not administered at all
- Severe violation of treatment compliance
  - Medical team will review subjects with treatment compliance outside 80% and 120% (refer to section 14.1) and decide if the violation is severe.
- Any deviation of inclusion/exclusion criteria should be considered as important violations.
- A severe violation to the restricted DMARD therapy (protocol table 4.2.2.1:1), as assessed by the medical team.

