## 16.3. LABORATORY EVALUATIONS

Results from the central laboratory will be included in the reporting of this trial for Serum Chemistry, Hematology and Urinalysis. A list of laboratory assessments to be included in the outputs is included in APPENDIX 4.

Presentations will use SI and US Units.

Quantitative laboratory measurements reported as "< X", i.e. below the lower limit of quantification (BLQ), or "> X", i.e. above the upper limit of quantification (ULQ), will be converted to X for the purpose of quantitative summaries, but will be presented as recorded, i.e. as "< X" or "> X" in the listings.

Qualitative laboratory urinalysis results measured by central laboratory will be classified to the categories "Positive" and "Negative" based on the central laboratory normal reference.

The handling of retests, unscheduled and end of trial measurements is described in Section 6.3. However, laboratory values taken after the first dose of trial medication up to a period of 10 weeks after the last dose of the trial medication will be assigned to the treatment phase for evaluation. All available data will be listed.

The following summaries will be provided for laboratory data:

- Actual and change from baseline in trial 1297.2 by visit (for quantitative measurements)

---

Document: \\ieedc-nas01a\BIOSdata\Boehringer\_Ingelheim\BI\_695501\NVA96235\Biostatistics\Documentation\SAP\10  
v1.0\BI\_1297.3\_SAP\_22JUN2016\_v1.0

Author: Version Number: 1.0  
Version Date: 22JUN2016

Template No: CS\_TP\_BS016 – Revision 3  
Effective Date: 01May2012

Reference: CS\_WI\_BS005

- Shifts in Rheumatology Common Toxicity Criteria (RCTC) grading, from baseline in trial 1297.2 by visit (for gradable parameters, see APPENDIX 4)
- Shifts from baseline category (Low/ Normal/ High) in trial 1297.2 by visit (for non-gradable parameters except urinalysis parameters and ADA)
- Shift from baseline category (Negative/ Positive) in trial 1297.2 by visit (for urinalysis non-gradable parameters)
- Box plots for ESR, CRP, hemoglobin, leukocytes (equivalent to white blood cells), platelets, AST, ALT, bilirubin, creatinine, cholesterol
- Plots for time course of gradable safety parameters for subjects having at least one value with toxicity grade 3 or 4 (RCTC grading is described section 16.3.3)
- Proportion and frequency of possible Hy's law subjects
- Proportion and frequency of possible Drug Induced Liver Injuries

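### Flow chart footnote 8 sets the transaminase exclusion at more than 3x ULN, twice the limit in exclusion criterion 21 (more than 1.5x ULN)

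*Protocol*

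**What the plan says.** The protocol gives a transaminase exclusion limit in two places.

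- Flow Chart, footnote 8, on the row for serum chemistry, hematology and urinalysis: "Findings of alanine aminotransferase or aspartate aminotransferase >3 times the upper limit of normal or hemoglobin <8.0 g/dL at baseline are criteria for exclusion".
- Section 3.3.3, criterion 21: "Aspartate aminotransferase (AST) or alanine aminotransferase (ALT) >1.5 times upper limit of normal (ULN". It names no visit. Criterion 22 repeats the footnote's hemoglobin limit.

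On which text decides entry, section 3.3.4.1 says that patients "who meet one or more of the exclusion criteria will not be enrolled in this extension trial". Section 6.2.1 places the decision at Screening: "Once patients have signed the ICF, completed screening, and eligibility is confirmed, the Investigator will contact IRT and patients will be assigned to treatment".

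The SAP says in section 9.1: "Any deviation of inclusion/exclusion criteria should be considered as important violations". These are listed for the assigned set. Section 5.4 adds: "No per protocol analysis set (PPAS) is defined in this trial".

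On contraception, inclusion criterion 4 reads: "Acceptable methods of birth control include, for example, birth control pills, intrauterine devices, surgical sterilization, vasectomized partner and double barrier method". Exclusion criterion 12 gives its own list in parentheses: intrauterine devices, surgical sterilization, double barrier and vasectomized partner. Pills are not on it.

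**The concern.** Footnote 8 restates two of the exclusion criteria. It gets hemoglobin right and gives transaminases at a different value, with no explanation. The flow chart is the schedule that sites work from, and the footnote sits on the row for the test being read, so the number there may be taken as the eligibility limit.

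A site that does so could admit a patient whom criterion 21 bars. That patient would start a further 48 weeks of a TNF inhibitor with raised transaminases, while required to stay on methotrexate at least to Week 12. Section 2.3 relies on cautious entry criteria to limit risk and singles out drug-induced liver injury for surveillance, so the limit matters for safety as well as for paperwork. The enrolment would also be reported as an important deviation that consistent wording would have prevented.

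**Working it through.** The plan states no figure to reproduce. The check compares the two limits and follows the consequences through the protocol and SAP.

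**1. The limits**

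| Item | Footnote 8 | Section 3.3.3 | Agree? |
|---|---|---|---|
| ALT or AST | >3x ULN, at baseline | >1.5x ULN, no visit named (criterion 21) | No |
| Hemoglobin | <8.0 g/dL, at baseline | <8.0 g/dL, no visit named (criterion 22) | Limit yes |

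Ratio of the transaminase limits: 3 / 1.5 = 2.

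**2. What each text does with a given value**

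| ALT or AST | Footnote 8 | Criterion 21 |
|---|---|---|
| Up to 1.5x ULN | does not exclude | does not exclude |
| Above 1.5x, up to 3x ULN | does not exclude | excludes |
| Above 3x ULN | excludes | excludes |

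Only the middle band is affected. A patient at exactly 3x ULN is not caught by the footnote, yet already meets the transaminase part of the combined hepatic injury definition in section 5.3.6 (at least 3x ULN, together with bilirubin at least 2x ULN).

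**3. Could the limits belong to different visits?** The words at the end of footnote 8 point to the Baseline visit (Day 1). Against that:

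- The flow chart marks the eligibility assessment at Screening only.
- Section 6.2.1 confirms eligibility and assigns treatment at Screening.
- The Day 1 procedure list in section 6.2.2 contains no eligibility recheck.
- The footnote mark is on the label of the whole laboratory row, which includes Screening.

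No text assigns 1.5x to one visit and 3x to the other. Global Amendment 01 edited both the flow chart and section 3.3.3 and changed neither limit.

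**4. Reach into the analysis.** SAP section 5 defines five sets:

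- ENR: consent
- ASD: assignment
- FAS: assignment, a dose and some efficacy data
- SAF: a dose
- PKFS: a dose and a valid concentration

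Definitions that depend on eligibility: 0 of 5. A patient enrolled against criterion 21 stays in every set whose conditions are met. SAP section 16.3 plans laboratory summaries as "Actual and change from baseline in trial 1297.2 by visit (for quantitative measurements", and the shift tables use the same 1297.2 reference, so the value at entry to 1297.3 is not their baseline.

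**5. Contraception.** Inclusion criterion 4 names five methods and presents them as examples. Exclusion criterion 12 names four, as a closed list. The difference, 5 - 4 = 1, is birth control pills. The conflict concerns sexually active premenopausal women able to conceive whose only method is the pill: one criterion accepts them and the other excludes them.

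**The case against.** The strongest reply is that the two texts do not strictly contradict each other. Anyone above 3x ULN is also above 1.5x ULN, so the footnote is true as far as it goes, and it never says that patients between the limits may enter. Meeting any one criterion bars enrolment, the flow chart has its own eligibility row without footnote 8, and section 6.2.1 sends sites to section 3.3. Read as a whole, the protocol gives one answer. This stands, and it lowers the chance of a wrong enrolment. It does not remove it: an explicit exclusion limit at twice the correct value remains on the laboratory row.

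A second reply is that the sponsor may have meant a stricter Screening limit and a looser Day 1 recheck. Laboratory tests are indeed repeated on Day 1, so the reading is possible. It is written nowhere, and if it is intended the protocol still has to say so.

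A third reply is that the trial is single-arm and descriptive, and hepatic injury is monitored as an event of special interest, so the consequence is small. That is fair for the statistics. One qualification runs the other way: Category 2 of the drug-induced liver injury definition in SAP section 16.3.1 uses multiples of a baseline value. Were that the 1297.3 baseline, a raised entry value would raise the bar for that category. This does not alter the conclusion on the footnote.

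The contraception mismatch is a separate matter and adds no weight to the transaminase point.

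**Conclusion.** The concern holds. Footnote 8 gives a transaminase limit twice that of criterion 21, and patients with ALT or AST above 1.5x and up to 3x ULN are excluded by one text and not by the other. Section 3.3.3 governs, so the footnote is the text that is wrong as written.

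The size is modest. The documents do not say how many patients fall in the band, and only those actually enrolled against criterion 21 become deviations. No analysis set is defined by eligibility, and the planned laboratory change and shift tables do not use the entry value as baseline. What is at stake is avoidable hepatic risk in individual patients and avoidable important deviations. The conclusion assumes that no unstated visit-specific rule exists; if one does, the fault becomes failing to state it, and a correction is still needed. It should be fixed.

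**What to change.** Change the transaminase limit in footnote 8 to more than 1.5x ULN, matching criterion 21. If the sponsor does want a looser Day 1 recheck, write in both footnote 8 and criterion 21 that 1.5x ULN applies at Screening and 3x ULN at Day 1.

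Separately, make inclusion criterion 4 and exclusion criterion 12 agree on whether oral contraception alone is acceptable.

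The cost is amendment wording for one footnote (plus criterion 21 if visit-specific limits are chosen) and one contraception list. No new assessment or analysis is needed.

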## **ABBREVIATIONS**

|          |  |
|----------|--|
| ACR      | American College of Rheumatology                       |
| ACR20    | American College of Rheumatology 20% response criteria |
| ACR50    | American College of Rheumatology 50% response criteria |
| ACR70    | American College of Rheumatology 70% response criteria |
| ADA(s)   | Antidrug antibody(ies)                                 |
| AE       | Adverse Event  |
| AESI     | Adverse Event of Special Interest                      |
| ALT      | Alanine aminotransferase                               |
| Anti-CCP | Anti-cyclic citrullinated peptide                      |
| AST      | Aspartate aminotransferase                             |
| BI       | Boehringer Ingelheim                                   |
| CRP      | C-reactive protein                                     |
| CTP      | Clinical Trial Protocol                                |
| CTR      | Clinical Trial Report                                  |
| DAS      | Disease Activity Score                                 |
| DAS28    | Disease Activity Score in 28 joints                    |
| DILI     | Drug-induced liver injury                              |
| DMARD    | Disease-modifying antirheumatic drug                   |
| ECG      | Electrocardiogram                                      |
| eCRF     | Electronic Case Report Form                            |
| EMA      | European Medicines Agency                              |
| EoT      | End of Treatment                                       |
| ESR      | Erythrocyte sedimentation rate                         |
| EU       | European Union   |
| EULAR    | European League Against Rheumatism                     |
| FAS      | Full Analysis Set                                      |
| FDA      | Food and Drug Administration                           |
| GCP      | Good Clinical Practice                                 |
| GH       | General Health   |
| HAQ-DI   | Health Assessment Questionnaire – Disability Index     |
| HBsAg    | Hepatitis B surface antigen                            |
| HBV      | Hepatitis B virus                                      |
| HCV      | Hepatitis C virus                                      |
| HEV      | Hepatitis E virus                                      |
| HIV      | Human immunodeficiency virus                           |
| IB       | Investigator's Brochure                                |
| ICH      | International Conference on Harmonisation              |
| IDMC     | Independent Data Monitoring Committee                  |
| IEC      | Independent Ethics Committee                           |
| IRB      | Institutional Review Board                             |
| IRT      | Interactive Response Technology                        |
| ISF      | Investigator Site File                                 |
| i.v.     | Intravenous  |
| LOCF     | Last observation carried forward                       |

|          |  |
|----------|--|
| MedDRA   | Medical Dictionary for Regulatory Activities   |
| MMP      | Matrix metalloproteinase   |
| MTX      | Methotrexate   |
| nADA     | Neutralizing ADAs  |
| NSAIDs   | Nonsteroidal anti-inflammatory drugs   |
| PK       | Pharmacokinetics   |
| PPK      | Population pharmacokinetic   |
| RA       | Rheumatoid arthritis   |
| REP      | Residual effect period, after the last dose of medication with measureable drug levels or pharmacodynamic effects still likely to be present |
| RF       | Rheumatoid Factor  |
| SAE      | Serious Adverse Event  |
| SC       | Subcutaneous   |
| SF-36 v2 | 36-item Short Form Health Survey version 2   |
| SFU      | Safety Follow-up   |
| SJC      | Swollen joint count  |
| SUSAR    | Suspected unexpected serious adverse reaction  |
| TB       | Tuberculosis   |
| TJC      | Tender joint count   |
| TNF      | Tumor necrosis factor  |
| TSAP     | Trial Statistical Analysis Plan  |
| ULN      | Upper limit of normal  |
| US       | United States of America   |
| VAS      | Visual analogue scale  |
| VCA      | Virus capsid antigen   |

